1) Male or female, ages 18-65; 2) medically stable; 3) >6 months post-SCI; 4) SCI affecting segments between C4-T12; 5) no other known neurological disorders; 6) no severe musculoskeletal impairments, open wounds, or skin lesions that would limit participation in functional assessments; 7) able to provide informed consent

Exclusion criteria:

1) Not meeting any of the above inclusion criteria; 2) presence of a self-reported uncontrolled medical condition including, but not limited to: cardiovascular disease; sleep apnea; obstructive lung disease; severe neuropathic or chronic pain; severe recurrent autonomic dysreflexia; 3) severe, untreated bladder or urinary tract infection; 4) women who report being pregnant or test positive on a pregnancy test.

We aim to screen 40 individuals with SCI and enroll 30 subjects in this study.

Recruitment and enrollment

The target population will be individuals with SCI. Study procedures will take place at Brooks Rehabilitation in Jacksonville, FL, and the University of Florida's Health Science Center Department of Physical Therapy Research Laboratories. Subjects will be recruited in four ways.

- 1) The study team will notify Brooks clinicians about the study via e-mail. The study team may also notify other clinicians who work with individuals with SCI through e-mail. Those clinicians may then notify their patients about the study, who may then contact [name], the principal investigator, or other study staff for more information.
- 2) Potential subjects also may be informed of the study via IRB approved flyers, which will be hung in the Brooks Health System, the Health Science Center at UF, and in the community. Contact information will be provided on the flyer so that interested potential subjects may contact [name] for more information.
- 3) Information regarding the study also may be provided through word of mouth or general presentations such as at support groups and community meetings (i.e. such as meetings for those with SCIs).

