Individuals who are potentially interested in enrollment in the study will have ample opportunity to ask questions, talk with study staff and review the informed consent document. If the individual indicates that he/she would like to determine if they qualify to participate in the study, they will be asked to complete a basic screening questionnaire to determine if they are eligible to participate. The screening may occur over the phone or in-person depending on the preference of the potential participant. The IRB-approved screening form, designed to avoid collection of protected health information, (see attached) will ask subjects general information about their eligibility. This information may include health status, physical functioning, history of neurologic impairments, the date of their SCI, and other information pertaining to inclusion/exclusion criteria. If an individual completes the screening process, is eligible to participate, and would like to enroll, a study staff member will meet with them to complete the informed consent process. The informed consent form (ICF) will be used to guide the process. The potential participant will have the opportunity to review the ICF ahead of time. Potential participants will be informed there may be no direct benefit of participation. Study staff will be available to answer questions. The informed consent process will occur prior to study procedures but may occur on the same visit as the anticipated study procedures. The informed consent process also may be scheduled on a day prior to study procedures based on the preference of the potential participant. We anticipate that some potential participants may want to meet with study staff ahead of time and others will prefer to complete the informed consent form and procedures on a single visit.

Participants may be asked to participate in the following activities during an assessment. They will be informed that they may choose not to perform any aspect of the study.

Overview

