This pilot study will utilize a single blind, placebo-controlled, randomized, repeated measures experimental design. Participants will be asked to come in for two visits at least 7 days apart. If study procedures are not completed in the two sessions (such as due to equipment malfunction or unexpected time restrictions/events), an additional session may be required to complete procedures. This will be scheduled at the participant's convenience. Participants will be asked to wear comfortable, casual clothing for participation ahead of time, during their phone screening. In the first visit, participants will be asked to complete a demographic health and function questionnaire. Questions may address their injury level, medical history, impact of their condition on physical functioning, breathing function, and their walking or other functional abilities. Participants may then be asked to undergo standardized assessments of muscle strength and sensory function. Following collection of this baseline information, the remainder of the first visit will be similar to all subsequent visits. Visits will include:

- Pre-assessments of respiratory strength, postural strength and function, EMG of trunk muscles, and trunk positioning using non-invasive sensors. For subjects who can stand or walk with assistance, ambulation assessments may be conducted while also recording trunk and lower extremity EMGs, and joint angles or forces using non-invasive sensors.
- 15 short exposures to hypoxic air, or a sham exposure, in a randomized order (details below)
- Post-assessments of respiratory strength, postural function, ambulation, EMG of trunk muscles, and trunk and joint positioning using non-invasive sensors

Each session will last about 3 hours and no longer than 6 hours. Rest breaks will be provided at regular intervals and at any time the participant requests. A study clinician will oversee the study procedures and monitor the participants, including a baseline assessment of vital signs (blood pressure, heart rate, and blood oxygen saturation) for safety.

For participants who provided consent for photography and/or video, recordings or photographs may be obtained during their session. Recordings or photographs will only occur based on the consent provided by each participant. The participant will be informed that they may refuse the use of photography or video recordings at any time during the procedures.

Study Procedures

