Participants will be asked not to ingest any caffeine within four hours of each visit, as caffeine can affect the response to acute intermittent hypoxia. After consenting, female subjects of potential childbearing age will be asked to take a pregnancy test. A pregnancy test will not be required if a medical condition that prohibits pregnancy, such as hysterectomy, is reported. Participants will be able to sit or lie on a mat table comfortably during set-up. Instrumentation will generally include EMG sensors over the trunk,

respiratory, and lower extremity muscles, which may be secured with hypoallergenic tape. Electrogoniometers to measure joint angles may be attached at the hips, knees, or along the vertebral column with double-sided medical tape. Pressure sensors also may be placed under the heel or ball of the subject's feet, and worn in the shoes. All sensors are non-invasive and will be removed at the conclusion of testing.

1) Baseline and demographic assessments:

Participants may undergo the ISNCSCI (International Standards for the Neurological Classification of Spinal Cord Injury) examination. The ISNCSCI is a standardized assessment used to determine the motor and sensory impairment and severity of a spinal cord injury (Kirshblum et al., 2011; previously known as the ASIA examination based on the American Spinal Injury Association). A study clinician will complete this assessment using standardized procedures. Subjects may also be asked general demographic information via and IRB-approved demographics form about their injury, rehabilitation history, current health status, and current activity and exercise levels.

2) Standardized assessments of respiratory function

These clinical tests of respiratory function will be administered according to standardized guidelines (American Thoracic Society, 2002; Miller et al., 2005). Clinical outcomes from these assessments will allow us to assess the level of respiratory function of subjects vs. predicted values derived from able-bodied individuals based on the subject's age. Participants will complete up to, but no more than 10 trials of each test in order to ensure a maximal effort was obtained. Rest breaks will be allowed at the subject's request as often and as long as they are needed. Oxygen saturation and breathlessness will be monitored for safety. The assessments may include:

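### No repeat of the pregnancy test is stated after the one requested at consent, so a woman randomised to sham first can receive hypoxia at visit 2 on an out-of-date result

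*Combined protocol and SAP*

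**What the plan says.** All references are to section 6 (Research Plan) of the combined protocol and SAP unless stated.

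- **Exclusion criteria.** Among those excluded are "women who report being pregnant or test positive on a pregnancy test" and people with "severe, untreated bladder or urinary tract infection". Self-reported uncontrolled medical conditions are also excluded. No time window is attached to any of these.
- **Recruitment and enrollment.** Before consent, interested people are screened by phone or in person: "they will be asked to complete a basic screening questionnaire to determine if they are eligible to participate". Consent can be taken at the same visit as the procedures, but "The informed consent process also may be scheduled on a day prior to study procedures". No maximum interval is given.
- **Study Procedures.** On the test itself: "After consenting, female subjects of potential childbearing age will be asked to take a pregnancy test". Women who report a condition that rules out pregnancy are exempt. No frequency is given. The sentence just before it applies the caffeine restriction to each visit.
- **Overview.** "Participants will be asked to come in for two visits at least 7 days apart", with no upper limit, and "an additional session may be required to complete procedures". A health and function questionnaire belongs to the first visit. The contents listed for every visit are pre-assessments, the exposure (hypoxia or sham, in randomised order) and post-assessments. A clinician oversees the procedures and takes baseline vital signs.

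**The concern.** Pregnancy is a condition that the plan treats as serious enough to test for, and not merely to ask about. A negative result describes the day on which it was obtained. The plan fixes that day by reference to consent, while the exposure that the exclusion guards against may come at visit 2, an unbounded time later. Someone following the text exactly would have no instruction to test again.

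A severe, untreated urinary infection can also arise between visits, and a medical condition that was controlled at screening can become uncontrolled. For these the plan has a rule but no scheduled question after visit 1.

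What is at stake is participant safety: whether the plan's own exclusions are checked on the day hypoxia is given. The exposure is 15 episodes at 9% to 15% inspired oxygen, with staff stepping in if SpO2 falls below 80%.

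**Working it through.** The plan gives no figure on this point to reproduce. The check sets the stated timings side by side and then counts who is affected.

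**1. What is checked, and when**

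| Step | Stated timing | Required again at visit 2? |
|---|---|---|
| Eligibility questionnaire | Before consent | No |
| Pregnancy test | After consent | No repeat stated |
| Health and function questionnaire | Visit 1 | No |
| Demographics form, may cover current health | Listed as a baseline assessment | No |
| Vital signs, clinician oversight, SpO2 | At sessions | Yes, but cannot detect pregnancy |
| Termination criteria (Safety monitoring) | During the session | Yes, but address acute reactions |

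**2. Age of the test at a visit-2 exposure**

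Let a be the days from the test to visit 1 and g the days from visit 1 to visit 2. If the test is taken at consent or at visit 1, then a ≥ 0, with a = 0 when both fall on the same day. The plan sets g ≥ 7.

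Age at visit 2 = a + g ≥ 0 + 7 = 7 days.

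Neither a nor g has a stated maximum, so the age has no upper limit. If a > 0, the result is also not same-day at visit 1.

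**3. Who receives hypoxia at visit 2**

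The enrolment target comes from the text following the exclusion criteria: "We aim to screen 40 individuals with SCI and enroll 30 subjects in this study". The allocation ratio for order is not stated; 1:1 is assumed.

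- All participants: 30 × 0.5 = 15 expected to have sham first and hypoxia at visit 2. Under simple randomisation the 2.5th to 97.5th percentiles of a binomial(30, 0.5) count are 10 and 20, and the probability of 10 to 20 is 0.957. Order ratios from 1:2 to 2:1 would give expected counts over the same range (30 × 1/3 = 10 to 30 × 2/3 = 20).
- Women tested: if w women are tested, w × 0.5 = w/2 are expected to receive visit-2 hypoxia on the test taken at consent or visit 1. The plan does not give w, so w/2 cannot be turned into a number; it is bounded above by 30/2 = 15.

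These are counts of people whose exposure has no stated same-day check. They are not counts of new pregnancies or infections, for which the documents give no rate.

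**4. Extra tests if a same-day test is required**

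- Consent and test on the day of visit 1: that test counts for visit 1, so one extra at visit 2, or w in total.
- Consent and test on an earlier day: one extra at each visit, or up to 2w in total.
- Any additional session that includes exposure adds one more for the woman concerned; the number of such sessions is not stated.

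**The case against.** The strongest reply is that the text is silent on repeats and does not exclude them. The instruction to test after consent fixes the earliest point, and the sentence stands beside steps that recur at each session, so staff may well repeat it. That is fair. A reader might infer that the plan specifies a single test, but the documents do not say so. They support only that no repeat is stated. If a test at each visit is intended, saying so resolves the point.

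A second reply is that the exclusions carry no expiry date. This also stands. A participant who reports a pregnancy or a newly uncontrolled condition at visit 2 still meets an exclusion, and the clinician present may notice illness. A reader might infer that the exclusions lapse after visit 1; they do not. What is missing is a step that prompts for them, and early pregnancy in particular may not be volunteered or visible.

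Third, only a severe and untreated urinary infection is excluded, so a mild or treated one is no reason to stop. Likewise, the additional session is described as completing procedures and may involve assessments alone. Both limits are accepted and carried into the fix.

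Fourth, section 7 calls the discomforts and risks of the procedure minimal, and nothing in the documents shows harm from exposure in early pregnancy. This limits the weight of the point but does not remove it, because the plan itself chose to exclude pregnancy and to test for it.

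Finally, the screening form and consent pages were not available for review and may contain visit-day instructions.

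**Conclusion.** The point holds as a gap in timing. The pregnancy test is tied to consent with no stated repeat, and a sham-first woman can receive hypoxia at visit 2 on a result at least 7 days old with no upper limit. For the other exclusions, the gap is the lack of a stated prompt after visit 1.

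The size is about w/2 women under an assumed 1:1 order, with w unknown. It would be tempting to say that half of all planned sessions (30 of 60) are unprotected. That figure only restates that visit 2 is one of two visits. It does not measure risk, and the pregnancy part applies only to the women tested.

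A reader might also infer a demonstrated harm or a threat to the trial's result. The documents support neither. No event rate is given and none is claimed here. Each visit has its own pre-assessment and the order is randomised, so a change in health between visits has no material effect on the comparison of hypoxia with sham. This is a cheap improvement for participant safety, conditional on the unseen forms not already covering it.

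**What to change.** Add to section 6, under Overview and Study Procedures, that before exposure at every session that includes hypoxia or sham, staff will:

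1. do a same-day pregnancy test for each woman to whom the test applies, with a test at same-day consent counting for visit 1;
2. ask briefly whether any exclusion criterion is now present, namely pregnancy, a severe untreated bladder or urinary tract infection, or a newly uncontrolled medical condition;
3. defer the session or withdraw the participant if so.

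An additional session used only for assessments would not need this. Applying the check before sham as well as hypoxia keeps it from revealing the condition.

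The cost is one or two extra pregnancy tests per woman tested, a few minutes of questions per session and occasional rescheduling. The sample size and analysis are unchanged.

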Acute intermittent hypoxia is a safe, non-invasive technique to improve muscle strength and activation after SCI. All sessions will be monitored by a study clinician with experience in both delivering acute intermittent hypoxia, and treating individuals with SCI. Hypoxic intervals will be delivered with a commercially available sports performance hypoxicicator. A unit capable of delivering a fraction of inspired oxygen ranging from 21%-9% will be used. Air will be delivered into a mask that will be secured comfortably over the subject's nose and mouth. An SpO₂ sensor that monitors oxygen saturation of the blood will be used to monitor the subject's response to hypoxic intervals; if the user's SpO₂ falls below 80% during a round of hypoxia, the fraction of inspired oxygen delivered by the hypoxicicator will be rapidly increased in order to bring the user's SpO₂ back over the safety threshold. 80% SpO₂ is adequate to induce the effects of hypoxia without causing adverse safety events (Trumbower et al., 2012; Hayes et al., 2014; Lynch et al., 2016; Navarrete-Opazo et al., 2016a, 2016b).

Acute intermittent hypoxia will be provided to the subject by delivering 15 brief exposures (60 to 120 seconds) of hypoxic air alternated with 15 brief exposures (60 to 120 seconds) of room air. The amount of oxygen delivered during hypoxic exposures may range from 15%-9% fraction of inspired oxygen, compared to 21% oxygen in normal atmospheric air. Various protocols have previously used intervals and oxygen concentrations within this range (Trumbower et al., 2012; Tester et al., 2014; Navarrete-Opazo et al., 2016b). To switch from hypoxic to room air, a four-way valve will be attached to the subject's mask which can allow air from the hypoxicator, or ambient air from the room to flow into the mask. The amount of oxygen delivered and the length of the hypoxic and room air exposures will be adjusted during the protocol to maintain safety, tolerability, and a consistent hypoxic response of the subject. The total time of all episodes of alternating room and hypoxic air will be between 30-45 minutes. Alternatively, a sham protocol will be administered in which 21% fraction of inspired oxygen will be delivered by the hypoxicator during hypoxic intervals, and room air will be delivered through the four-way valve during room air intervals.

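### Do 15 + 15 exposures of 60 to 120 seconds contradict the stated total of 30 to 45 minutes, leaving hypoxia and sham undefined?

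*Combined protocol and SAP*

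**What the plan says.** All the relevant statements are in section 6 (Research Plan), under the heading on delivering acute intermittent hypoxia or a sham procedure.

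- Exposures: hypoxia is given by "delivering 15 brief exposures (60 to 120 seconds) of hypoxic air alternated with 15 brief exposures (60 to 120 seconds) of room air".
- Total: "The total time of all episodes of alternating room and hypoxic air will be between 30-45 minutes".
- Titration: "The amount of oxygen delivered and the length of the hypoxic and room air exposures will be adjusted during the protocol to maintain safety", and also for tolerability and a steady response to hypoxia.
- Oxygen level: "The amount of oxygen delivered during hypoxic exposures may range from 15%-9% fraction of inspired oxygen".
- Sham: "a sham protocol will be administered in which 21% fraction of inspired oxygen will be delivered by the hypoxicator during hypoxic intervals", with room air through the valve in the remaining intervals. No separate lengths or total are given for the sham.

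The Overview in the same section repeats the count of 15, for hypoxia or sham, and plans two visits at least 7 days apart. The Statistical Plan compares pre-to-post changes between the two conditions with t-tests and does not use session duration.

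**The concern.** A reader who multiplies the exposures by their longest permitted length gets an hour, while the next lines of the protocol stop at 45 minutes. Two figures that describe one procedure and do not multiply out suggest that one of them is wrong. The stated maximum also equals 30 exposures of 90 seconds, which hints that the interval range and the total were not worked out together.

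If the two statements did conflict, an operator on long intervals would have to break one of them, either by running over time or by giving fewer than 15 pairs. Dose and time on the mask could then vary between participants. They could also vary between the two visits of one participant, because hypoxia intervals follow the participant's response and the sham produces no such response to follow. That would add noise to a within-person comparison and might tell a participant which condition was being given.

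**Working it through.** **Inputs**, all from the delivery subsection of section 6: 15 hypoxic exposures of *h* seconds, 15 room-air exposures of *r* seconds, *h* and *r* each from 60 to 120, and a stated total of 30 to 45 minutes.

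**Formula:** total minutes = 15 × (*h* + *r*) / 60.

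| *h* (s) | *r* (s) | Total (min) | Within 30–45? | Hypoxic time (min) |
|---|---|---|---|---|
| 60 | 60 | 30 | yes | 15 |
| 90 | 90 | 45 | yes | 22.5 |
| 120 | 60 | 45 | yes | 30 |
| 60 | 120 | 45 | yes | 15 |
| 120 | 90 | 52.5 | no | 30 |
| 90 | 120 | 52.5 | no | 22.5 |
| 120 | 120 | 60 | no | 30 |

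**Stated figure.** The lower bound of 30 minutes reproduces. The upper bound from the interval range alone is 60, not 45: an excess of 15 minutes, and 15/45 = 33%.

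**When both statements hold.** A total of at most 45 minutes over 30 exposures requires a mean exposure of at most 45 × 60 / 30 = 90 seconds, that is, an average pair of at most 180 seconds. If *h* and *r* are held constant at whole seconds, there are 61 × 61 = 3,721 permitted pairs, of which 1,891 (51%) stay within 30 to 45 minutes. The two sentences therefore overlap over about half of the permitted range, before counting sessions in which lengths change along the way.

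**Must an operator on long intervals break a rule?** Only if both gases run long. At 120 seconds throughout, 45 × 60 / 120 = 22.5, so 22 complete exposures (11 pairs) fit in 45 minutes. With 120 seconds of one gas and 60 of the other, all 15 pairs fit exactly. No text permits fewer than 15 exposures in order to meet the time.

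**Does 45 minutes imply a 90-second upper interval?** Not uniquely: 30 × 90 seconds and 15 × (120 + 60) seconds both give 45 minutes. Section 4 (Background) describes one earlier study with 15 exposures of 60–90 seconds alternated with 15 of 60 seconds, which is 15 × 120 / 60 = 30 to 15 × 150 / 60 = 37.5 minutes. It describes another with 15 of 90 seconds alternated with 15 of 90 seconds, which is 15 × 180 / 60 = 45 minutes. Together these span the stated total, so it may have come from them, but that is inference.

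**What depends on 45 minutes?** The target of 30 participants, the t-tests, the outcome list and the 80% oxygen-saturation threshold are all stated without reference to it. Reassessment follows a 30-minute rest counted from the end of delivery, so a longer delivery does not shorten that interval.

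**The case for a change.** The strongest reply is that the protocol never calls the total a limit on the choice of intervals. It asks for lengths to be adjusted for safety, tolerability and response, fixes the count at 15, and does not say which figure gives way if adjustment carries the session past 45 minutes. About half of the permitted constant settings (1,830 of 3,721, or 49%) do carry it past. The sham sentence has its own gap: it gives the gas and the valve routing but no lengths. Titration to a hypoxic response has no counterpart under 21% oxygen, so the text does not say how sham timing is chosen. In a single-blind study where each participant is to have both conditions, that is a fair question.

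Both omissions are real, but they are omissions of detail. A range for each interval together with a range for the session is a coherent way to specify a titrated procedure, and staff can meet both without difficulty. The sham is written in terms of the same hypoxic and room-air intervals, so the natural reading is the same structure with a different gas. If both visits keep to the stated total, mask time can differ between them by at most 45 − 30 = 15 minutes. Nothing in the documents shows that participants would infer their condition from such a difference. The background reports that participants in earlier studies could not, or mostly could not, tell sham from hypoxia, although those studies did not test this particular cue.

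Nor would tidying the total make delivery uniform. Most of the variation comes from the deliberate adjustment within sessions and from the 9%–15% oxygen range. Even inside 45 minutes, cumulative hypoxic time can run from 15 to 30 minutes.

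**Conclusion.** The multiplication is correct: the interval range allows up to 60 minutes against a stated maximum of 45. The inference that the intervention and its sham are inconsistently defined is not correct. The two statements can be met together whenever the mean exposure is at most 90 seconds, and in-session adjustment gives staff the means to do so. A session that respects both gives sound data, and no design or analysis quantity moves with the 45-minute figure.

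What remains is missing detail of the kind that staff fill sensibly: whether the total binds, and that sham visits follow the same timing pattern as hypoxia visits. The sponsor may reconcile the wording when the text is next opened. Which figure stands is a clinical decision on which I take no view.

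This conclusion assumes that the total is read as a limit on the session as a whole, and that the sham is run on the same interval structure as hypoxia. The effect of a difference in mask time on the outcomes cannot be estimated from the documents.
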